6.7. Patient Characteristics

6.7.1. Demographics and Baseline Characteristics

Demographics and baseline characteristics including clinical, and health outcome measurements will be summarized by treatment group and overall for the ITT and Open-label Treatment Populations. Refer to the definition of baseline in Section 6.1.2.

Categorical data for baseline variables will be summarized as frequency counts and percentages. Continuous data for baseline variables will be summarized in using descriptive statistics: number of observations, mean, standard deviation, minimum, maximum, and median. Treatment group comparisons will be conducted using Fisher’s exact test for categorical data and an analysis of variance (ANOVA) model with treatment as a factor for continuous data.

By-patient listings of demographic and baseline characteristics, respectively, for the ITT population will be provided.

The following demographic and baseline characteristics will be summarized:

Demographics and Baseline Characteristics

- Sex (male, female)
- Age (in years)
- Age Categories: (<65, ≥65 to <75, ≥75 years) and (<40, ≥40 years)
- Weight (in kg)
- Weight Category: (<80, ≥80 to <100, ≥100 kg) and (<90 kg, ≥90 kg)
- Height (cm)
- Waist circumference (cm)

- Body Mass Index (BMI) (in kg/m²)
- BMI category: (underweight [<18.5 kg/m²]; normal [≥ 18.5 and <25 kg/m²]; overweight [≥ 25 and <30 kg/m²]; obese [≥ 30 and <40 kg/m²]; obese class III [≥ 40 kg/m²])
- Alcohol use: (never, current, former)
- Caffeine use: (never, current, former)
- Tobacco use: (never, current, former)
- Race (American Indian or Alaska Native, Asian, Black or African American, Native Hawaiian or Other Pacific Islander, White, Multiple)
- Ethnicity (Hispanic or Latino, Not Hispanic or Latino, Not applicable)
- Geographic region (US [including Puerto Rico], non-US)
- Country
- Previous non-biologic systemic therapy: (Never used, Used)
- Previous biologic therapy: (Never used, Used)
- Age at onset of Psoriasis (Ps)
- Age at onset of Genital Psoriasis
- Duration of disease (in years) –
 - Duration of Genital Ps since onset = [Date of informed consent – Date of onset of Genital Ps]/365.25
 - Duration of Ps since onset = [Date of informed consent – Date of onset of psoriasis]/365.25
 - Duration of Ps since diagnosed = [Date of Visit 2 – Diagnosis Date of psoriasis]/365.25
- Sociodemographics – marital and sexual partner status

Clinical and Health Outcome Measurements taken at Baseline

- sPGA for Genitalia
- sPGA for Genitalia category: (3, 4, 5)
- overall sPGA
- overall sPGA category: (3, 4, 5)
- mGPASI score
- overall Psoriasis Area and Severity Index (PASI) score
- overall PASI category: (<20 , ≥ 20)

- Psoriatic arthritis: (yes, no)
- Nail psoriasis: (yes, no)
- Scalp psoriasis: (yes, no)
- Presence of Psoriasis on the face: (yes, no)
- Presence of Psoriasis on inframammary fold: (yes, no)
- Presence of Psoriasis on axilla: (yes, no)
- Presence of Psoriasis on pubis: (yes, no)
- Presence of Psoriasis on inguinal creases: (yes, no)
- Presence of Psoriasis on gluteal cleft: (yes, no)
- Presence of Psoriasis on perianal region: (yes, no)
- BSA (%)
- BSA category: (<10%, ≥10%)
- Fitzpatrick skin type: (Types I, II, III, IV, V, VI)
- GPSS
 - Total score
 - Genital Ps Itch NRS score
 - Other individual item scores
- GPSIS subscales
 - Sexual Activity Avoidance Subscale
 - Impact of Sexual Activity on Genital Psoriasis Symptoms Subscale
- Sexual Frequency Questionnaire (SFQ) item scores
- Patient's Global Assessment of Genital Psoriasis (PatGA-Genital) score
- Touch avoidance NRS score
- Short Form 36 Question Health Survey (SF-36)
 - Physical Component Summary (PCS) score
 - Mental Component Summary (MCS) score
 - Domain Scores:
 - Physical Functioning
 - Role Physical
 - Bodily Pain

- General Health
- Vitality
- Social Functioning
- Role Emotional
- Mental Health
- DLQI
 - Total score
 - DLQI Item 9 score
 - DLQI total score of 0 or 1: (yes, no)
- Quick Inventory of Depressive Symptomatology–Self-Report 16 items (QIDS-SR16) total score
- QIDS-SR16 Item 12: 0, 1, 2, 3
- Columbia-Suicide Severity Rating Scale (C-SSRS) categories and composite scores as defined in Section 6.15.7
- Comprehensive Assessment of the Psoriasis Patient (CAPP) (genital sub-index)

6.7.2. Historical Illnesses and Pre-existing Conditions

Historical illnesses and pre-existing conditions will be classified using the latest version of the Medical Dictionary for Regulatory Activities (MedDRA).

Historical illness/condition is defined as the condition/event recorded on the Pre-existing Conditions and Medical History electronic case (clinical) report form (eCRF) page or on the Pre-specified Medical History eCRF page with an end date prior to the date of informed consent.

A pre-existing condition is defined as the condition/event recorded on the Pre-existing Conditions and Medical History eCRF page or on the Pre-specified Medical History eCRF page with a start date prior to the date of informed consent, and no end date (that is, the event is ongoing) or an end date on or after the date of informed consent. Notice if a pre-existing condition worsens in severity on or after the date of informed consent, it will be recorded as an AE on AE eCRF page from the date of worsening onwards.

The following summaries will be provided for the ITT Population:

- The number and percentage of patients with historical illnesses by treatment group and overall, by System Organ Class (SOC) and preferred term (PT).
- The number and percentage of patients with pre-existing conditions by treatment group and overall, by SOC and PT.
- The number and percentage of patients with pre-specified medical history (hypertension; diabetes mellitus, Type I; diabetes mellitus, Type II insulin dependent; diabetes mellitus

Type II non-insulin dependent; coronary artery disease; stroke; dyslipidemia; psoriatic arthritis; Crohn's disease; ulcerative colitis; Psoriasis) by treatment group and overall.

For a condition/event that is gender-specific (as defined by MedDRA), the denominator and computation of the percentage will include only patients from the given gender. The comparisons among treatment groups will be conducted using Fisher's exact test.

By-patient listings of historical illnesses and pre-existing conditions, respectively, for the ITT population will be provided.

6.8. Previous and Concomitant Therapy

A medication/therapy will be classified into anatomical therapeutic chemical (ATC) drug classes using the latest version of the World Health Organization (WHO) drug dictionary.

A by-patient listing of previous and concomitant therapy and a by-patient listing of previous psoriasis therapy and previous genital psoriasis therapy will be provided for the ITT Population.

6.8.1. Previous Therapy

Previous therapy is defined as the therapy that starts and ends prior to the date of first dose of study treatment in the Blinded Treatment Period (Period 2). If therapy start and/or end dates are missing or partial, the dates will be compared as far as possible with the date of first dose of study treatment in Period 2. If there is clear evidence to suggest that the therapy stopped prior to the first dose of study treatment in Period 2, the therapy will be assumed to be previous only.

The following summaries will be provided for the ITT population:

- Previous therapy (as captured in the Prior Therapy: Psoriasis eCRF page, the Prior Therapy: Genital Psoriasis Entry – Topical Therapy eCRF page, the Concomitant Therapy eCRF page and the Concomitant Therapy: Lipid Modifying Agents eCRF page) by WHO ATC Level 4 and WHO preferred term.
- Previous Psoriasis therapy (captured in the Prior Therapy: Psoriasis eCRF page) to be summarized according to type (non-biologic systemic agent, biologic agent, non-biologic non-systemic agent, phototherapy) and therapy. The previous biologic agent will be further classified as TNF- α inhibitor (includes infliximab, etanercept, adalimumab, golimumab, certolizumab pegol), interleukin (IL) 12/23 inhibitor (includes ustekinumab), IL-17 inhibitor (includes secukinumab), and other (includes efalizumab, alefacept, or other biological agent).
- The number and percentage of patients with each reason for discontinuation of previous Psoriasis therapy will be summarized by type and therapy.
- Previous Genital Psoriasis therapy captured in the Prior Therapy: Genital Psoriasis Entry – Topical Therapy eCRF page to be summarized according to therapy (Corticosteroids, Calcineurin Inhibitors, Vitamin D Analogs and Other Prescription Topicals).

- The number and percentage of patients with each reason for discontinuation of previous Genital Psoriasis therapy will be summarized by therapy. The number of prior genital psoriasis topical therapies taken by patients will also be summarized using the following categories: 0, 1, 2 and ≥ 3 .

Treatment group comparisons for the Blinded Treatment Period will be performed on the ITT population using Fisher's exact test.

6.8.2. Concomitant Therapy

Concomitant therapy for Period 2 is defined as the therapy that starts before, on, or after the first day of study treatment of Period 2 and before the last visit date of Period 2, and continues into Period 2, that is, either no end date is present (the therapy is ongoing) or the end date is on or after the first day of study treatment of Period 2. Note that, a concomitant therapy will belong to Period 2 if the therapy starts and ends on the exact same day as the first day of study treatment of Period 2.

Concomitant therapy for the Open-label Treatment Period (Period 3) is defined as the therapy that starts before, on, or after the last visit date of Period 2 and continues into Period 3, that is, either no end date is present (the therapy is ongoing) or the end date is after the last visit date of Period 2. Concomitant therapy will belong to Period 3 if the therapy starts and ends on the exact same day as the first day of study treatment of Period 3.

Concomitant therapy for the Post-Treatment Follow-up Period (Period 4) is defined as the therapy that starts before, on, or after the last visit date of Period 3 and continues into Period 4, that is, either no end date is present (the therapy is ongoing) or the end date is after the last visit date of Period 3. Concomitant therapy will belong to Period 3 if the therapy starts and ends on the exact same day as the last visit date of Period 3.

The following summaries will be provided:

- Concomitant therapy (as captured in the Concomitant Therapy eCRF page and the Concomitant Therapy: Lipid Modifying Agents eCRF page) by WHO ATC Level 4 and WHO preferred term using the ITT population for the Blinded Treatment Period and the Open-label Treatment Period, using the Open-label Treatment Population for the Open-label Treatment Period and using the Post-Treatment Follow-up Population for the Post-Treatment Follow-Up Period.
- The number and percentage of patients taking concomitant therapy of topical product to be summarized for topical and topical steroid therapies, respectively, by WHO ATC Level 4 and WHO PT for the ITT population during the Blinded Treatment Period. The definition of concomitant topical therapy can be found in Appendix 5 of the Ixekizumab Program Safety Analysis Plan Version 7 (IXE PSAP V7). Please refer to I1F-MC-RHBQ (b) Clinical Protocol Section 6.8 for concomitant therapies permitted during the study.
- The number and percentage of patients who received premedication for allergic reaction/hypersensitivity captured in the Allergic / Hypersensitivity Reaction Follow-up

eCRF page during the Blinded Treatment Period (Period 2) will be summarized for the ITT Population.

Treatment group comparisons for the Blinded Treatment Period will be conducted on the ITT Population using Fisher's exact test.

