5.1. Overview of Study Design

Study I1F-MC-RHBQ (RHBQ) is a Phase 3, multicenter, randomized, double-blind, placebo-controlled, parallel-group, outpatient study examining the efficacy and safety of ixekizumab as compared to placebo in patients with moderate-to-severe genital psoriasis. The study consists of 4 periods:

- **Period 1: Screening Period** (Visit 1 and Visit 1A) will assess patient eligibility and start e-diary data collection, occurring approximately 7 to 30 days prior to Period 2 (baseline; Week 0; Visit 2).
- **Period 2: Blinded Treatment Period** will occur from Week 0 (Visit 2) up to Week 12 (Visit 7). Patients will be randomized to ixekizumab or placebo in a 1:1 ratio. Two injections of ixekizumab 80 mg subcutaneous (SC) (total dose of 160 mg) or 2 injections of placebo SC, respectively, will be given at Week 0 (Visit 2). From Week 2 through Week 10 patients will receive ixekizumab 80 mg every 2 weeks (Q2W) SC or placebo Q2W SC.
- **Period 3: Open-Label Treatment Period** will occur from Week 12 (Visit 7) up to Week 52 (Visit 12). At Week 12 (Visit 7) 1 injection of ixekizumab 80 mg SC and 1 injection of placebo SC (total dose of ixekizumab 80 mg) will be given to patients who were randomized to ixekizumab in Period 2; and 2 injections of ixekizumab 80 mg SC (total dose of ixekizumab 160 mg) will be given to patients who were randomized to placebo in Period 2. During the remainder of Period 3, patients will receive ixekizumab 80 mg every 4 weeks (Q4W) dosing with an option to step-up to Q2W dosing starting at Week 24 through Week 40 (at Visit 9 [Week 24], Visit 10 [Week 28], or Visit 11 [Week 40]). This Open-label Treatment Period will allow evaluation of long-term efficacy and safety of ixekizumab through 1 year (52 weeks).
- **Period 4: Post-Treatment Follow-up** (Visit 801 through Visit 803) is for safety monitoring after treatment discontinuation for any patient receiving at least 1 dose of investigational product. Once patients complete the study treatment or discontinue study treatment early, patients will complete the Post-Treatment Follow-up (Period 4). For patients who have entered Period 4, psoriasis therapy is allowed, as determined appropriate by the investigator. This period occurs from the last treatment period visit or early termination visit (ETV) up to a minimum of 12 weeks following that visit.

Figure RHBQ.5.1 illustrates the study design.

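### SAP 6.8.2 sets no latest start date for Period 3 concomitant therapy, so follow-up therapies also count as open-label therapy, and the Period 4 rule is undefined for patients who stop in Period 2

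*SAP*

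**What the plan says.** SAP 6.8.2 assigns each therapy to a study period by comparing its dates with visit dates.

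- **Period 2.** The therapy "starts before, on, or after the first day of study treatment of Period 2 and before the last visit date of Period 2". It must also be ongoing, or end on or after the first dosing day.
- **Period 3.** The therapy "starts before, on, or after the last visit date of Period 2 and continues into Period 3". Continuing into the period is then spelled out as having no end date, "or the end date is after the last visit date of Period 2".
- **Period 4.** The therapy "starts before, on, or after the last visit date of Period 3 and continues into Period 4", spelled out as having no end date, "or the end date is after the last visit date of Period 3".

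A closing sentence in the Period 4 paragraph gives one-day therapies taken on the date of the last Period 3 visit to Period 3.

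The same section then lists populations for the summary: "using the ITT population for the Blinded Treatment Period and the Open-label Treatment Period", the Open-label Treatment Population for Period 3 as well, and the Post-Treatment Follow-up Population for Period 4.

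On follow-up treatment, SAP 5.1 states: "For patients who have entered Period 4, psoriasis therapy is allowed, as determined appropriate by the investigator". The Schedule of Activities (protocol Appendix 2) records concomitant medications at Visits 801, 802 and 803. Both database locks include follow-up data (protocol 9.9, SAP 6.18).

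**The concern.** The Period 3 rule opens at the last Period 2 visit and never closes. A start date before, on or after a given day is any date at all, so only the end-date test does any work, and a drug first taken after Week 52 passes it.

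Protocol Table RHBQ.6.2 does not permit biologics, systemic nonbiologic psoriasis therapy or phototherapy in Periods 1 to 3. A Period 3 table that lists them would suggest prohibited treatment behind the open-label results, when in fact the drug was properly started once the patient had left treatment.

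Patients who stop in Period 2 raise a second problem. They go through the ETV straight into follow-up and have no Period 3 visit, yet the Period 4 rule uses that visit as its only anchor. They do belong in the Period 4 tables. The Post-Treatment Follow-up Population in SAP 6.1.1 includes them, and Table RHBQ.6.1 gives Period 4 a placebo group, which can only be placebo patients who left before any open-label dose.

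**Working it through.** No figure in the plan depends on this rule, so the check is to write the rules out as tests and apply them to example therapies.

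Let *s* be the start date, *e* the end date (or none), F2 the first dosing day, and L2 and L3 the patient's last visits in Periods 2 and 3.

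- Period 2: *s* < L2, and (no *e*, or *e* ≥ F2).
- Period 3: (*s* < L2, *s* = L2 or *s* > L2), which is always true, and (no *e*, or *e* > L2).
- Period 4: the start test is again always true, and (no *e*, or *e* > L3).

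Days 84 (Week 12) and 364 (Week 52) are the scheduled days in protocol Appendix 2. The dropout days (196 and 40) and all therapy dates are assumed for illustration. For a patient who stops in Period 2, L2 is taken to be the ETV.

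The corrected rules are:

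- Period 3: the patient entered Period 3, *s* ≤ L3, and (no *e*, or *e* > L2).
- Period 4: no *e*, or *e* > LT, where LT is the last treatment-period visit or ETV.

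| Patient and therapy | Period 3 as written | Period 4 as written | Period 3 corrected | Period 4 corrected |
|---|---|---|---|---|
| Completer, days 200–220 | yes | no | yes | no |
| Completer, days 378–400 | yes | yes | no | yes |
| Completer, day 378, ongoing | yes | yes | no | yes |
| Stops in Period 3 (L3 = 196), days 210–240 | yes | yes | no | yes |
| Stops in Period 2 (ETV day 40), days 50–70 | date rule met | undefined: no L3 | no | yes |
| Stops in Period 2 (ETV day 40), day 50, ongoing | date rule met | met by the no-end-date branch, anchor missing | no | yes |

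None of these therapies meets the Period 2 rule. For example, in row 2 the Period 3 test is 400 > 84 and the Period 4 test is 400 > 364; both are true. In row 5 the Period 3 test is 70 > 40, true, but the Period 4 test compares 70 with a date that does not exist.

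The last two rows reach a Period 3 table only through its population. SAP 6.1.1 puts every Period 3 analysis on the Open-label Treatment Population, which requires a Period 3 dose. Protocol 9.4.3 summarizes medications for patients who enter each treatment period. SAP 6.8.2 nevertheless also names ITT for Period 3. On the ITT version, a placebo patient who left in Period 2 and never received ixekizumab can appear as having open-label concomitant therapy.

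**The case against.** The best defence is that the intent is clear. In ordinary language, a drug first taken in Period 4 does not continue into Period 3. The sentence on one-day therapies also shows that the authors saw the last Period 3 visit as the end of that period. This stands as evidence of intent. It does not settle how the table will be built, because the SAP replaces the ordinary meaning with an explicit date test, and that test is what would be programmed. The Period 2 rule shows that a start-date cap was thought necessary there.

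Part of the problem is already contained. The Open-label Treatment Population version of the Period 3 summary excludes everyone who stopped in Period 2, and SAP 6.8 provides a by-patient listing from which therapy dates can be checked.

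A reader might also infer more than the text supports:

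- *That follow-up therapies are moved out of Period 4.* For patients with a Period 3 visit they also meet the Period 4 rule. The fault is double counting.
- *That therapies of patients who stop in Period 2 are excluded from Period 4.* The rule is undefined for them. Ongoing therapies meet the no-end-date branch; the fate of the rest depends on how a missing anchor is programmed.
- *That every psoriasis drug shown would look prohibited.* Table RHBQ.6.2 permits several topical products in Period 3 outside the genital area.
- *That uneven dropout would bias a comparison of arms.* Table RHBQ.6.1 plans no comparison in Periods 3 or 4. Neither nonresponder imputation (SAP 6.3.1) nor the neutrophil recovery analysis (SAP 6.15.4.2) uses this classification.

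**Conclusion.** The concern holds as a drafting error in three linked places: an open-ended Period 3 rule, a Period 4 anchor that patients who stop in Period 2 do not have, and an ITT-based Period 3 summary that conflicts with SAP 6.1.1 and protocol 9.4.3. It is minor. It affects the descriptive concomitant-therapy tables for Periods 3 and 4, and leaves the Period 2 rule, the primary and major secondary tests and the sample size untouched.

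The number of patients affected cannot be derived, because the documents give no rates for uptake of therapy in follow-up or for dropout. For scale only, assume that 120 of the 146 patients enter follow-up from Period 3 and that 30% to 60% start some new therapy there. Then 120 × 0.30 = 36 to 120 × 0.60 = 72 patients would have a therapy counted in both periods. Not all of these would be drug classes prohibited in Period 3. If 10% stop in Period 2, 146 × 0.10 = 14.6, or about 15 patients, would have no Period 4 anchor. All of these rates, and the 120, are assumptions.

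**What to change.** Make three wording changes in SAP 6.8.2:

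1. Add to the Period 3 rule that the therapy must start on or before the patient's last Period 3 visit, and apply the rule only to patients who entered Period 3. The limit should be on or before, because strictly before would contradict the sentence that gives one-day therapies on that date to Period 3. A drug started on the visit day itself and continued will still count in both periods; a footnote can say so.
2. Anchor the Period 4 rule on the patient's last treatment-period visit: Week 52, or the ETV in Period 2 or Period 3.
3. Run the Period 3 summary on the Open-label Treatment Population only, as SAP 6.1.1 requires, and delete the reference to ITT for that period.

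The cost is a short SAP edit and matching table specifications. No new data are needed, since therapy and visit dates are already collected.

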6.9. Treatment Compliance

By-patient listings of randomization schedule and study drug dispensed (including the clinical trial [CT] Lot number), for the ITT Population will be provided.

Throughout the Blinded Treatment Period (Period 2), randomized patients will record information in a Study Drug Administration Log (captured in the Exposure eCRF page), including the date, time, and anatomical location of administration of investigational product, syringe number, who administered the investigational product, and the reason if the investigational product was not fully administered.

Treatment compliance for each patient will be calculated as:

$$\textit{Treatment Compliance \%} = 100 \times \frac{\textit{Total number of injections administered}}{\textit{Total number of injections prescribed}}$$

- For patients who complete Period 2, the total number of injections prescribed during Period 2 will be equal to 7 (2 injections at Week 0 and 1 injection every 2 weeks from Week 2 to Week 10).
- For patients who discontinue during Period 2, the number of injections prescribed can be derived from the IWRS study drug dispense dataset.
- For patients who complete Period 3, the expected number of injections will be calculated as follows:
 - For patients who remain on Q4W dosing for the entire Open-label Treatment Period, the total number of injections prescribed during Period 3 will be equal to 11 (2 injections at Week 12 and 1 injection every 4 weeks from Week 16 to Week 48). The last dose will be administered at Week 48.
 - For patients who switch to Q2W dosing after Week 24, the total number of injections prescribed during Period 3 will be calculated as

$$2 + \frac{(x - 12)}{4} + \frac{(50 - x)}{2}$$

where x is the week at which the patient switched to Q2W dosing and x can assume values 24, 28 or 40. The last dose will be administered at Week 50.

- For patients who discontinue during Period 3, the number of injections prescribed can be derived from the IWRS study drug dispense dataset.

- The total number of injections administered will be derived using the response to the question “Was dose administered?” on the Exposure eCRF page.

A patient will be considered compliant overall for each study period if he/she misses no more than 20% of the expected doses, does not miss 2 consecutive doses, and does not overdose (that is, take more injections at the same time point than specified in the protocol).

Patient treatment compliance during the Blinded Treatment Period and the Open-label Treatment Period will be summarized for the ITT population and the Open-label Treatment Population, respectively. Proportions of patients compliant overall will be compared between treatment groups during Period 2 using Fisher’s exact test.

A by-patient listing of study treatment administration and compliance for the ITT Population will be provided.

